Statistical Methods	
All analyses will be exploratory in character and all assessed measures will be analyzed. Continuous variables will be summarized by number (N), mean, standard deviation (SD), minimum, 5% percentile (P5), lower quartile (Q1), median, upper quartile (Q3), 95% percentile (P95) and maximum. Categorical variables will be presented in frequency distribution tables with number (N) and percentage. All endpoint assessments with more than two time points will be tabulated by timepoint and displayed graphically for absolute values and change from baseline values.
 
[REDACTED]

	
If there is a substantial rate of patients with rescue medication ($n > 20$), explorative subgroup analyses will be provided for patients with and without rescue medication.
 
Populations for statistical analyses:
 
Safety (SAF) population: All enrolled patients who received at least one instillation of Cystistat and validity of data is confirmed by the physician.
 
Full analysis set (FAS) population: All patients of the SAF, who have at least one post baseline assessment.

[figure not shown]
	Interim analysis: 
--	--

Table 0-1 Study Schedule

STUDY DAY	Baseline ¹⁾	During Treatment	End of Treatment ²⁾	Follow-up ³⁾
	Before first treatment	Week 1-11 (as per standard of care)	Latest Week 12 (Month 3)	Approximately Month 6
Written informed consent	X			
Demography and medical history ⁴⁾	X			
In-/exclusion criteria	X			
Patient Global Assessment of overall IC/BPS condition improvement ⁵⁾			X	X
Assessment of BPIC-SS ⁶⁾	X		X	X
Assessment of VAS ⁷⁾	X		X	X
Instillation of Cystistat ⁸⁾		X	X	(X)
Dispense of diary card ⁹⁾	X		X	
Review of diary card		X	X	X
Collection of diary card			X	X
Assessment of concomitant medications ¹⁰⁾		X	X	X
Assessment of adverse events, incidents ¹¹⁾	X	X	X	X

¹⁾ Baseline assessments may be performed on the first treatment visit prior to instillation of Cystistat according to routine clinical practice.

²⁾ This assessment will be performed on the last treatment day or latest at week 12; if required, treatment will be continued after week 12 under regular medical care.

³⁾ Follow-up will be performed as an on-site visit if in accordance with routine clinical practice; if not possible as an on-site visit, the information will be collected remotely (e.g., via phone and postal mail) from the patient.

⁴⁾ Demography and medical history:

- Patients' demographic and anamnestic background data

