- Diagnostic criteria of IC/BPS diagnosis
- Previous and current treatments

⁵⁾ Patient Global Assessment of overall IC/BPS condition improvement: To be completed at end of treatment or latest at week 12 and at month 6.

⁶⁾ Bladder Pain/ Interstitial Cystitis Symptom Score (BPIC-SS): To be completed prior to the first treatment, at end of treatment or latest at week 12, and at month 6.

⁷⁾ Visual Analogue Scale (VAS) for bladder pain, urinary urgency, and quality of life (QoL): To be completed prior to first treatment, at end of treatment or latest at week 12, and at month 6.

⁸⁾ Instillation of Cystistat: Cystistat will be instilled into the bladder according to the instructions for use; the regimen and duration of treatment will depend on the investigators' discretion; each instillation of Cystistat until month 6 will be recorded in the eCRF; the observation period for this study will end approximately at month 6 (irrespective of the duration of treatment); if required, treatment will be continued after month 6 under regular medical care.

⁹⁾ Diary card: The following assessments are to be filled out by the patient:

- Morning voiding volume once a week, preferably on the treatment day (until end of treatment or latest week 12) and once at month 6
- Urinary voids and the respective volumes over a period of 24 hours once a week, preferably starting the day before the treatment day (until end of treatment or latest week 12) and once at month 6
- Use of concomitant IC/BPS medication, pain medication, and other relevant concomitant medication (until month 6)
- Adverse events (until month 6)

¹⁰⁾ The use of concomitant IC/BPS medication, pain medication, and other relevant concomitant medication will be recorded; it is not required to collect all concomitant medication

¹¹⁾ Adverse events and incidents will be recorded after first instillation of Cystistat; prior to first instillation of Cystistat only adverse events will be recorded.

SIGNATURE PAGE

Protocol Title Real-world evidence observational study to evaluate performance and safety of intravesical sodium hyaluronate (Cystistat®) in the treatment of patients with interstitial cystitis (IC)/bladder pain syndrome (BPS)

Protocol Number CYST-SLZ-7001

Version 1.0

Protocol Date 06-Apr-2022

Clinical Sciences Lead (Author):

[REDACTED] [REDACTED] [REDACTED]
[REDACTED] Urology, Allergy
Global Clinical Sciences

Safety Lead (Reviewer):

[REDACTED] [REDACTED] [REDACTED]
[REDACTED] Global Parapharmaceutical

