3.3 End of Study Definition

The end of study is defined as the date of the last visit (or remote contact) of the last patient included in the study.

Cystistat will be instilled into the bladder according to the instructions for use (13). The observation period for a patient in this study will end approximately 6 months after start of treatment (irrespective of the duration of treatment). If required, treatment will be continued thereafter under regular medical care.

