6 STUDY CONDUCT

When the clinical decision has been made to prescribe Cystistat for the first time to a patient according to the instructions for use (13), the investigator will consider enrolling the patient into this NIS. The decision to prescribe Cystistat must be previous and independent from the decision to include the patient in the NIS.

Patients eligible for study recruitment will have the nature, purpose, and risks of the study explained to them by the investigator. They will be provided with a written copy of the informed consent form (ICF) for the study and given sufficient time to consider the study's implications before deciding to participate. Patients agreeing to participate in the study will sign the ICF and be given a duplicate copy before recording any personal data.

In cases where the patient does not return to the next routine treatment, the site should make every effort to contact the patient so that they can appropriately be withdrawn from the study. All contact attempts should be documented in the patient's medical record. Should the patient continue to be unreachable, then she will be considered to have withdrawn from the study as "Lost to Follow-up." For all other patients withdrawing from the study, an alternative reason for discontinuation should be recorded in the eCRF. Patients may voluntarily withdraw from the trial for any reason and at any time.

In this NIS, the intended duration of observation per patient is approximately 6 months after start of treatment (irrespective of the duration of treatment). For details and timings of assessments, refer to [Section 7.0](#) and [Table 0-1](#).

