- If required, treatment with Cystistat will be continued thereafter under regular medical care. For all patients, a follow-up visit will be scheduled for approximately month 6.

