6.4 Follow up (approximately at Month 6)

Follow-up will be performed as an on-site visit if in accordance with routine clinical practice; if not possible as an on-site visit, the information will be collected remotely (e.g., via phone and postal mail) from the patient.

Procedures will be completed in the following order:

- The investigator will collect the paper diary card and transcribe the information recorded by the patient into the eCRF. The paper diary card will be stored with the patient's medical record.
- The investigator will assess and record any adverse events that occurred since the last visit.
- The investigator will record any concomitant use of IC/BPS medication, pain medication, and other relevant concomitant medication that were taken since the last visit; it is not required to collect all concomitant medication.
- Patients will be asked to complete the Bladder Pain/Interstitial Cystitis Symptom Score (BPIC-SS).
- Patients will be asked to complete the Patient Global Assessment (PGA).
- Patients will be asked to complete the Visual Analogue Scale (VAS) for pain.
- The investigator will assess and record any adverse events and incidents, including any related adverse events, use error, and malfunction (see "incident" definition, [Section 10.1](#)), that occurred until or during this visit. All adverse events and incidents must be transmitted to the sponsor via the eCRF (see [Section 10.4.1](#) for reporting requirements).

Special focus will be posed on the side effects listed in the instructions for use of the investigational device: allergic reaction (local rash and/ or itching), bladder/urethral pain and discomfort, or urinary tract infection.

- The investigator will enter all required data from this visit in the eCRF within 5 business days. Specific reporting requirements for AEs and incidents are described in [Section 10.4.1](#).

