6.5 Withdrawal and Early Termination

Patients may request termination of the treatment with the investigational medical device or withdrawal from the study at any time or be required to withdraw or terminate treatment with the investigational medical device by the investigator or sponsor for reasons as per [Section 4.2.3](#). If the patient terminates early, withdraws or is withdrawn, the reason for early termination/withdrawal should be established and recorded.

If a patient does not return for a scheduled visit, every effort should be made to contact the patient. In any circumstance, every effort should be made to document the outcome of patient contact attempt, if possible. The investigator will contact sponsor or designee in the event that a patient fails to complete the study.

Every effort should be made to complete the following procedures and obtain the data from the patients:

- The investigator will collect the paper diary card and transcribe the information recorded by the patient into the eCRF. The paper diary card will be stored with the patient's medical record.

- The investigator will assess and record any adverse events that occurred since the last visit.
- Patients will be asked to complete the Bladder Pain/Interstitial Cystitis Symptom Score (BPIC-SS).
- Patients will be asked to complete the Patient Global Assessment (PGA).
- Patients will be asked to complete the Visual Analogue Scale (VAS) for bladder pain, urinary urgency, and quality of life (QoL)
- The investigator will enter all required data for withdrawal/early termination in the eCRF within 5 business days. If withdrawal is due to an AE or incident, please consider specific reporting requirements described in [Section 10.4.1](#).

If the patient withdraws from the study and also withdraws consent for disclosure of future information, no additional data should be collected. The sponsor may retain and continue to use any data collected before such withdrawal of consent.

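### Protocol section 6 turns a missed routine treatment into a step towards study withdrawal, against the plan's own follow-up to month 6, and leaves the exit PGA without a remote route or an analysis rule

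*Protocol*

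**What the plan says.** **Missed treatment.** Protocol section 6 covers the patient who does not come back for her next routine treatment: the "site should make every effort to contact the patient so that they can appropriately be withdrawn from the study". The paragraph then gives two outcomes. A patient who cannot be reached is classed as lost to follow-up; for every other patient leaving the study, a reason is recorded. It describes no patient who stops instillations and stays under observation.

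**Follow-up.** Section 3.3 says that observation "will end approximately 6 months after start of treatment (irrespective of the duration of treatment"), and section 6 repeats this two sentences after the withdrawal wording. Section 6.3 adds: "For all patients, a follow-up visit will be scheduled for approximately month 6". Under section 6.4, "if not possible as an on-site visit, the information will be collected remotely". Section 4.2.3 treats ending treatment and withdrawing from the study as two different options.

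**Timing of the primary PGA.** Table 0-1, footnote 2: "This assessment will be performed on the last treatment day or latest at week 12". Footnote 8 says that "the regimen and duration of treatment will depend on the" investigator's discretion. Neither Table 0-1 nor section 6.2 has a PGA at the week 1 to 11 visits.

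**Early stopping.** Section 6.5 deals with early termination, withdrawal and failure to attend. "Every effort should be made to complete the following procedures and obtain the data from the patients", it says, and it lists the diary, adverse events, BPIC-SS, PGA and all three VAS scales. Collection stops only if the patient also withdraws consent to future disclosure. SAP 5.12, which has the early termination visit in its title, says only that the reason will be recorded.

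**Analysis.** SAP 7.1 divides responders by all FAS patients, and SAP 7.2 applies the same method at month 6. SAP 5.11 uses observed data with no imputation.

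**The concern.** The section 6 instruction and the follow-up plan point in different directions. A site that follows section 6 literally closes the record of a patient who has only stopped treatment. A site that follows sections 3.3 and 6.3 keeps her to month 6. Sites may differ, and the difference falls on patients whose stopping is likely to be related to outcome: they feel well, they see no benefit, or they had an adverse event.

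Two sets of data are exposed. The first is everything due at month 6 (PGA, BPIC-SS, VAS) and the adverse events after withdrawal, because section 10 collects adverse events only until the patient's last study visit or contact. The second is the primary PGA. When a patient stops without notice, nobody knew at the last instillation that it was the last, so no PGA was taken then. It has to be obtained afterwards, from someone who is not attending, and the SAP gives no rule for using it.

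**Working it through.** **Step 1: follow one patient through the text.** Suppose that she has her fifth instillation and does not return.

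- At visit 5 no PGA is scheduled (Table 0-1, section 6.2).
- Section 6: the site contacts her with the stated aim of withdrawing her.
- Section 6.5: the site tries to obtain PGA, BPIC-SS and VAS. No route other than attendance is named; phone and post appear only for the month-6 contact (Table 0-1 footnote 3, sections 4.2.3 and 6.4).
- Month 6: sections 3.3 and 6.3 imply that she is still followed. Section 6.5 does not say so for a patient already withdrawn, and the section 6.3 sentence stands within a visit that she may never have.
- Analysis: her voiding diary is a secondary endpoint, so one usable post-baseline entry puts her in the FAS as SAP 5.2.3 defines it. She is in the denominator whether or not a PGA exists. If one is obtained, SAP 5.12 does not say which visit it belongs to.

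**Step 2: the plan's own dropout figure.** The SAP adds 7 patients for about 10% dropout before end of treatment or week 12, to reach 74. The implied base is 74 − 7 = 67. 67 × 1.10 = 73.7, rounded up to 74, so the figure reproduces; 67 / 0.90 = 74.4 would round up to 75. The derivation of 67 is redacted. About 10% is the only figure in the documents for how many patients stop early.

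**Step 3: bound for the primary rate.** Let x be the observed responders, m the FAS patients without a PGA and N the FAS size. Reported rate = x/N. The true rate lies between x/N and (x + m)/N, so the largest shortfall is m/N. Assume N = 74, m = 7 (all planned dropouts without a PGA, which section 6.5 is meant to prevent) and an observed rate near 60%, 70% or 85% (the protocol cites remission rates of 60 to 85%):

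| x of 67 | x/67 | x/74 (reported) | (x + 7)/74 |
|---|---|---|---|
| 40 | 59.7% | 54.1% | 63.5% |
| 47 | 70.1% | 63.5% | 73.0% |
| 57 | 85.1% | 77.0% | 86.5% |

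The largest shortfall is 7/74 = 9.5 points. For scale, the 90% Wald half-width at n = 67, 1.645 × √(p(1 − p)/67), is 9.8 points at 60%, 9.2 at 70% and 7.2 at 85%. (The plan's interval method is redacted; Wald is used only for scale.)

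**Step 4: month-6 rate, worst-case illustration.** All counts are assumed: FAS of 70, 10 patients withdrawn under section 6 with no month-6 PGA, 39 of the other 60 responding. Reported: 39/70 = 55.7%.

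| Responders among the 10 | True rate | Shortfall |
|---|---|---|
| 0 | 39/70 = 55.7% | 0 |
| 4 | 43/70 = 61.4% | 5.7 points |
| 8 | 47/70 = 67.1% | 11.4 points |
| 10 | 49/70 = 70.0% | 14.3 points |

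**Step 5: score changes.** BPIC-SS and VAS use observed values only. If the withdrawn patients did badly, the responder rate is right, but the mean improvement can look better than it was. The documents give no figure from which to size this.

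**The case against.** A reader might infer that the outcomes of patients who stop treatment are simply not collected. The documents do not support that. Section 6.5 names the patient who fails to attend and asks for every effort to obtain PGA, BPIC-SS and VAS. Month 6 is scheduled for everyone and may be done remotely. The section 6 paragraph can be read as disposition tracking only. Nor can one say that unannounced stopping is common: sections 4.2.3 and 6.2 describe weekly visits up to week 12, and the only figure is about 10% dropout.

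Other points on that side:

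- The endpoint text and section 6.3 allow the PGA at end of treatment or by week 12, so one obtained on contact before week 12 arguably already qualifies. This is reasonable, but the SAP should say so.
- Remote collection at early stopping is not forbidden. True; it is a silence. But it concerns patients who by definition did not attend.
- The SAP fits one mixed model over both time points for the scores, so a patient with an exit BPIC-SS still contributes. This softens the point on scores for patients with an exit value, but not for those with neither value.
- SAP 7.1 allows sensitivity analyses for dropouts, and SAP 7.3 adds an available-data subgroup if more than 10 patients terminate early. Neither recovers an outcome that was not obtained, and the first is optional.
- The percentages in Step 4 assume that month-6 follow-up fails for all ten patients. Agreed: they are a worst case and not a forecast.

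What the objection does not remove is the stated purpose of the contact in section 6, which conflicts with sections 3.3, 4.2.3 and 6.3 as they stand.

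**Conclusion.** The concern holds in a limited form. Section 6 makes a missed routine treatment a step to study withdrawal, and this cannot be reconciled with observation to about month 6 or with the separation of treatment termination from study withdrawal. For the primary PGA the risk is a late or incomplete value with no stated analysis rule; planned non-collection is not what the protocol describes. The firmer loss is at month 6: patients withdrawn under section 6 would have no month-6 PGA, BPIC-SS or VAS and no later adverse events, and a missing month-6 PGA then counts as non-response.

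The size depends on how sites apply the paragraph, which the documents cannot tell us. On the assumed counts the month-6 rate is 5.7 to 14.3 points too low if 4 to 10 of 10 withdrawn patients were responders, and correct if none were. For the primary rate the ceiling at the planned dropout is 9.5 points, and section 6.5 should keep it below that. Both rest on the visible text of SAP 7.1; parts of that section are redacted. This is a cheap improvement: it does not invalidate the design.

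**What to change.** - **Protocol section 6:** replace the purpose clause of the sentence on missed treatments. The patient is contacted to establish whether treatment has ended and to complete the section 6.5 assessments. She remains in observation to month 6 unless she withdraws from the study or another section 4.2.3 reason for not completing it applies.
- **Protocol section 4.2.3:** reconcile the wording with this and leave its list of reasons unchanged. It separates the two kinds of stopping, yet lists an event that warrants treatment withdrawal among the reasons for not completing the study. Study withdrawal should not be narrowed to withdrawn consent or loss of contact, because that would contradict this section.
- **Protocol sections 6.3 and 6.5:** allow the phone and postal route already given in section 6.4, and record the date on which each questionnaire was completed.
- **SAP 5.12:** state that a PGA obtained in this way up to week 12 is the end-of-treatment value.

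The cost is a few sentences and some extra questionnaires by an existing route. The downside is that some end-of-treatment PGAs will be remote and some days after the last instillation, which the completion date makes visible. One limit is timing: the protocol plans to finish in Q3 2023 and the SAP is dated 30 November 2023. If the study ran to plan, the collection changes come too late and only the SAP rule can still help.

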6.1 Baseline (before first treatment)

Patients for whom Cystistat is prescribed by the treating investigator will be enrolled in the study after signing a written informed consent form. No personal data will be recorded for the study before the consent procedure. Once eligible patients provide written informed consent, baseline assessments will be completed (this may be performed on the first treatment visit prior to instillation of Cystistat according to routine clinical practice):

- The investigator will review and document the patient's demography and medical history. This includes patients' demographic and anamnestic background data, diagnostic criteria of IC/BPS diagnosis, and previous and current treatments.
- Patients will be asked to complete the Bladder Pain/ Interstitial Cystitis Symptom Score (BPIC-SS). If the score is ≤ 18 , the patient will not be suitable for entering this NIS.
- The investigator will evaluate if the patient meets the inclusion/exclusion criteria.
- Patients will be asked to complete the Visual Analogue Scale (VAS) for bladder pain, urinary urgency, and quality of life (QoL).
- The investigator will assess and record any adverse events that occurred during this visit after signing the informed consent form.
- The investigator will provide the patient with the diary card and instruct her on how to record study related data at home. The following assessments are to be filled out by the patient:
 1. Morning voiding volume (once a week, preferably on the treatment day)
 2. Urinary voids and the respective volumes over a period of 24 hours (once a week, preferably starting the day before the treatment day)
 3. Use of concomitant IC/BPS medication, pain medication, and other relevant concomitant medication
 4. Adverse events
- A date for the next visit for the first treatment with Cystistat will be arranged and the investigator will remind the patient not to forget to take the diary card with her that day (not required if the first treatment with Cystistat is performed during the same visit according to routine clinical practice).
- The investigator will enter all required data from this visit in the eCRF within 5 business days.

6.2 During Treatment (Week 1-11, as per standard of care)

The patient will visit the site on a weekly basis for the instillation of Cystistat according to the instructions for use (13). The first treatment with Cystistat may be performed during the same visit as for the baseline assessments according to routine clinical practice (in this case not all of the below mentioned procedures need to be performed at the first treatment visit).

At each visit, procedures will be completed in the following order:

- The investigator will review the paper diary card, copy new entries, and transcribe the information recorded by the patient into the eCRF (not required at first treatment visit if performed on same visit as for the baseline assessment).
- The investigator will assess and record any adverse events that occurred since the last visit (not required at first treatment visit if performed on same visit as for the baseline assessment).
- The investigator will record any concomitant use of IC/BPS medication, pain medication, and other relevant concomitant medication that were taken since the last visit; it is not required to collect all concomitant medication (not required at first treatment visit if performed on same visit as for the baseline assessment).
- Cystistat will be instilled into the bladder according to the instructions for use and as per standard of care.
- The investigator will assess and record any adverse events and incidents, including any related adverse events (side effects), use errors, and malfunction (see “incident” definition, [Section 10.1](#)), that occurred during or between the visits. All adverse events and incidents must be transmitted to the sponsor via the eCRF (see [Section 10.4.1](#) for reporting requirements).

Special focus will be posed on the side effects listed in the instructions for use of the investigational medical device: allergic reaction (local rash and/or itching), bladder/urethral pain and discomfort, or urinary tract infection.

- The investigator will re-dispense the diary card to the patient and instruct her on how to record study related data at home. The following assessments are to be filled out by the patient:
 1. Morning voiding volume (once a week, preferably on the treatment day)
 2. Urinary voids and the respective volumes over a period of 24 hours (once a week, preferably starting the day before the treatment day)
 3. Use of concomitant IC/BPS medication, pain medication, and other relevant concomitant medication
 4. Adverse events(not required at first treatment visit if performed on same visit as for the baseline assessment)
- A date for the next visit for the next treatment with Cystistat will be arranged and the investigator will remind the patient not to forget to take the diary card with her that day.
- The investigator will enter all required data from this visit in the eCRF within 5 business days. Specific reporting requirements for AEs and incidents are described in [Section 10.4.1](#).

